### Bausch & Lomb Incorporated Study #875

and for each subject's final on-treatment visit.

- Proportion of study eyes with complete resolution of AC cells and flare at each visit and for each subject's final on treatment visit.
- Change from baseline in AC cells and flare, combined and separately, at each follow-up visit.

#### Safety Endpoints

The safety endpoints for this study are:

- Incidence of ocular and non-ocular AEs
- Change in IOP
- Ocular signs (biomicroscopy)
- Change in VA
- Change in dilated fundus exam

#### Tolerability Endpoints

The tolerability endpoints for this study are:

- Study drug sensation assessment at Visit 5 (Postoperative Day 8)
- Ocular symptoms at each follow-up visit

#### General Statistical Considerations

Summaries for continuous variables will include the sample size, mean, SD, median, minimum, and maximum. Minimums and maximums will be reported with the same precision as the raw values; medians and means will have 1 more decimal place; SD will have 2 more decimal places. Summaries for discrete variables will include the tabulation of frequencies and percentages. Differences between treatment groups will be calculated as LE gel 0.38% minus vehicle, and change from baseline will be calculated as follow-up visit minus baseline. The baseline visit will be defined as Visit 3 (Postoperative Day 1). For IOP, change from the previous visit will also be summarized.

#### Hypotheses

The following multiple endpoints and multiple dose-vehicle comparison hypotheses will be tested using Bonferroni-based tree structured gatekeeping tests to control the overall type I error rate ( $\alpha = 0.05$ ) for the primary efficacy endpoints over the entire study. The hypotheses in Family 1 will be tested simultaneously. Each hypothesis in Family 2 will be eligible for rejection only if the corresponding hypothesis (TID, BID) in Family 1 is rejected.

#### *Family 1 of Hypotheses: Complete Resolution of AC Cells in the Study Eye at Visit 5*

$H_{011}$ : The difference, between subjects treated with LE gel 0.38% dosed TID and subjects treated with vehicle, in the proportion of subjects with complete resolution of AC cells in the study eye at Visit 5 (Postoperative Day 8) = 0.

$H_{A11}$ : The difference, between subjects treated with LE gel 0.38% dosed TID and subjects treated with vehicle, in the proportion of subjects with complete resolution of AC cells in the study eye at Visit 5 (Postoperative Day 8) does not equal 0, with superiority claimed if the difference favors LE gel 0.38% dosed TID.

$H_{012}$ : The difference, between subjects treated with LE gel 0.38% dosed BID and subjects treated with vehicle, in the proportion of subjects with complete resolution of AC cells in the study eye at Visit 5 (Postoperative Day 8) = 0.

### Bausch & Lomb Incorporated Study #875

$H_{A12}$ : The difference, between subjects treated with LE gel 0.38% dosed BID and subjects treated with vehicle, in the proportion of subjects with complete resolution of AC cells in the study eye at Visit 5 (Postoperative Day 8) does not equal 0, with superiority claimed if the difference favors LE gel 0.38% dosed BID.

#### ***Family 2 of Hypotheses: Complete Resolution of Pain in the Study Eye at Visit 5***

$H_{021}$ : The difference, between subjects treated with LE gel 0.38% dosed TID and subjects treated with vehicle, in the proportion of subjects with Grade 0 pain in the study eye at Visit 5 (Postoperative Day 8) = 0.

$H_{A21}$ : The difference, between subjects treated with LE gel 0.38% dosed TID and subjects treated with vehicle, in the proportion of subjects with Grade 0 pain in the study eye at Visit 5 (Postoperative Day 8) does not equal 0, with superiority claimed if the difference favors LE gel 0.38% dosed TID.

$H_{022}$ : The difference, between subjects treated with LE gel 0.38% dosed BID and subjects treated with vehicle, in the proportion of subjects with Grade 0 pain in the study eye at Visit 5 (Postoperative Day 8) = 0.

$H_{A22}$ : The difference, between subjects treated with LE gel 0.38% dosed BID and subjects treated with vehicle, in the proportion of subjects with Grade 0 pain in the study eye at Visit 5 (Postoperative Day 8) does not equal 0, with superiority claimed if the difference favors LE gel 0.38% dosed BID.

#### **Analysis of Primary Efficacy Endpoints**

The primary efficacy endpoints are the proportion of subjects with complete resolution of AC cells at Visit 5 (Postoperative Day 8) and the proportion of subjects with Grade 0 pain at Visit 5 (Postoperative Day 8). Primary efficacy analyses will be based on the intent-to-treat (ITT) population with missing data imputed as failures (subjects placed on rescue medication prior to the visit being summarized will also be considered failures).

The primary efficacy analyses of the difference between each active treatment group and the combined vehicle treatment group at (Visit 5) Postoperative Day 8 will be tested using Pearson Chi-squared tests with p-values adjusted using a Bonferroni-based tree gatekeeping strategy. Null hypotheses with adjusted p-values  $\leq 0.05$  will be rejected.

95% confidence intervals will be constructed around the treatment differences using asymptotic normal approximations.

As a supportive analysis, these endpoints will be tested using the asymptotic Cochran Mantel-Haenszel statistic adjusting for site.

Supportive analyses of the primary analysis will be repeated on the per-protocol (PP) set.

#### **Analysis of Secondary Efficacy Endpoints**

Analyses of secondary efficacy endpoints will be based on the ITT population. Missing data from subjects who are rescued or have discontinued the study prior to a study visit will be handled by either of two approaches: 1) missing data are imputed as failures; or 2) the last observation prior to the rescue medication or subject discontinuation is carried forward to subsequent visits (LOCF).

With the exception of change from baseline to each follow-up visit, each of the secondary efficacy endpoints will be independently tested at each visit using similar statistical methods employed for primary efficacy endpoints (without the p-value adjustments).

Bausch & Lomb Incorporated Study #875	

Change from baseline (Visit 3) in AC cells and flare composite score (Anterior Chamber Reaction), as well as individual cells and flare scores, will be analyzed using both continuous and discrete statistical methods by treatment and visit, with missing data imputed by LOCF.
 
Analysis of complete resolution of AC cells, and Grade 0 pain at each visit will be conducted using a Pearson Chi-squared test, with missing data imputed as failures, and also with missing data imputed by LOCF. Similar analyses will be performed for complete resolution of AC cells and flare combined and for flare separately.
 
Other secondary or exploratory efficacy analyses may also be carried out as described in the study Statistical Analysis Plan.
 
Safety Endpoints
 
Tolerability endpoints will be summarized using discrete summary statistics by visit and treatment group.
 
Treatment-emergent AEs (TEAEs), defined as AEs that occur after the first dose of study medication, will be summarized prior to and after rescue medication and as ocular and non-ocular events separately. Ocular events will be summarized for treated eyes and fellow eyes separately. Non-treatment-emergent events will be presented only in the listings, with ocular and non-ocular events displayed separately.
 
A 95% confidence interval around the difference between treatment groups in the incidence of treatment-emergent AEs >1% will be constructed using asymptotic normal approximations.
 
Biomicroscopy and Fundoscopy
 
Biomicroscopy findings will be summarized at each visit and at the worst case on treatment by subject and parameter, both prior to and after rescue medication use. Incidence of treatment-emergent events will be tested using both a Pearson Chi-squared test and a Cochran Mantel-Haenszel test
 
Fundoscopy measures will be summarized for screening and at Visit 6 (Postoperative Day 15) or upon study exit for early termination, for all subjects and subjects that had no rescue medication use. Incidence of treatment-emergent events will be tested using a Pearson Chi-squared test and a Cochran Mantel-Haenszel test adjusted for study sites.
 
Visual Acuity
 
Pinhole Snellen VA will be summarized at each visit as a categorical variable (20/20, 20/40, etc) and as a line change from baseline (Visit 3). Worst line change from baseline will also be presented. Visual acuity will be presented prior to and after rescue medication use. Subjects presenting a line change of >2 lines will be tested using a Pearson Chi-squared test and a Cochran Mantel-Haenszel test adjusted for study sites.
 
IOP
 
Intraocular pressure will be summarized at each visit and worst case on treatment for each subject using both continuous summaries (including change from baseline [Visit 3]) and discrete summaries. Results prior to and after rescue medication use will be presented separately. Discrete summaries will include:
 
 
• The proportion of subjects with change in IOP from screening at any visit <math>\geq 5</math> and <math>\geq 10</math> mm Hg
 
• The proportion of subjects with change in IOP from baseline at any visit
 
	

Bausch & Lomb Incorporated Study #875	
	
(Visit 3) <math>\geq 5</math> and <math>\geq 10</math> mm Hg
 

• The proportion of subjects with treatment-emergent IOP <math>\geq 30</math> mm Hg

• IOP at each visit categorized into: <math>\leq 5</math>, 6 to 14, 15 to 21, 22 to 29, and <math>\geq 30</math>

• Change from screening in IOP at each visit categorized into: <math>\leq -5</math>, -4 to 0, 1 to 4, 5 to 9, 10 to 14, and <math>\geq 15</math>

• Change from baseline (Visit 3) in IOP at each visit categorized into: <math>\leq -5</math>, -4 to 0, 1 to 4, 5 to 9, 10 to 14, and <math>\geq 15</math>

 
Ocular Symptoms and Study Drug Sensation
 
Ocular symptoms will be summarized at each visit and presented by treatment separately for data obtained prior to receiving rescue medication and for data obtained after receiving rescue medication.
 
Study drug sensation data collected at Visit 5 (Postoperative Day 8) will be summarized by treatment group.
 
Tolerability endpoint analyses will use the Safety population with actual treatment received.

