#### 6.2.3.1     Rescue Medication

Subjects will be assessed at Visits 4 through 7 (Postoperative Days 3, 8, 15, and 18) for treatment rescue. Subjects with worsening or no change in the grade of inflammation in the study eye compared with the previous visit are eligible and may be considered for rescue medication. For subjects who meet either of these criteria, it is at the discretion of the Investigator when to begin rescue medication. The choice of rescue medication and dosing shall also be determined by the Investigator. Subjects requiring rescue medication for inflammation will stop treatment with the study drug and will be promptly discontinued from the study. The inflammation will not be reported as an adverse event (AE). The rescue medication will be recorded on the Concomitant Medication electronic case report form (eCRF) and the exit reason will be entered as “rescue medication” in the eCRF. Subjects who receive rescue medication will be counted as treatment failures as of the date of receiving rescue medication. Subjects who require rescue medication should return within 7 days following the date that rescue medication begins in order to undergo the procedures for the early termination visit.

NOTE: Rescue med that is required at V7 will not be recorded on the ConMed eCRF

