## 8.5 Statistical Analysis

### 8.5.1 Methods of Analysis

Summaries for continuous variables will include the sample size, mean, SD, median, minimum, and maximum. Minimums and maximums will be reported with the same precision as the raw values; medians and means will have 1 more decimal place; SD will have 2 more decimal places. Summaries for discrete variables will include the tabulation of frequencies and percentages. Differences between treatment groups will be calculated as LE gel 0.38% minus vehicle, and change from baseline will be calculated as follow-up visit minus baseline. The baseline visit will be defined as Visit 3 (Postoperative Day 1). For IOP, change from the previous visit will also be summarized.

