### Analysis of Secondary Efficacy Endpoints

Analyses of secondary efficacy endpoints will be based on the ITT population. Missing data from subjects who are rescued or have discontinued the study prior to a study visit will be handled by either of two approaches: 1) missing data are imputed as failures; or 2) the last observation prior to the rescue medication or subject discontinuation is carried forward to subsequent visits (LOCF).

With the exception of change from baseline to each follow-up visit, each of the secondary efficacy endpoints will be independently tested at each visit using similar statistical methods employed for primary efficacy endpoints (without the p-value adjustments).

Change from baseline (Visit 3) in AC cells and flare composite score (Anterior Chamber Reaction), as well as individual cells and flare scores, will be analyzed using both continuous and discrete statistical methods by treatment and visit, with missing data imputed by LOCF.

Analysis of complete resolution of AC cells and Grade 0 pain at each visit will be conducted using a Pearson Chi-squared test, with missing data imputed as failures, and also with missing data imputed by LOCF. Similar analyses will be performed for complete resolution of AC cells and flare combined and for flare separately.

Other secondary or exploratory efficacy analyses may also be carried out as described in the study Statistical Analysis Plan.

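### Change from baseline in AC cells, flare and composite is imputed only by LOCF, which carries rescued eyes' pre-rescue grade to Day 15 and, if vehicle eyes are rescued more often, is likely to overstate the LE effect there

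*Combined protocol and SAP*

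**What the plan says.** The synopsis and section 8.5.1.1 (Analysis of Secondary Efficacy Endpoints) say that change from baseline in the AC cells and flare composite, and in each score separately, "will be analyzed using both continuous and discrete statistical methods by treatment and visit, with missing data imputed by LOCF". The value carried is defined in the same place: "the last observation prior to the rescue medication or subject discontinuation is carried forward to subsequent visits (LOCF"). Baseline is Visit 3, Postoperative Day 1 (section 8.5.1).

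The complete-resolution endpoints are treated differently. They are analysed "with missing data imputed as failures, and also with missing data imputed by LOCF".

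Section 6.2.3.1 fixes who can be rescued: "Subjects with worsening or no change in the grade of inflammation in the study eye compared with the previous visit are eligible". It also fixes what happens next: "Subjects requiring rescue medication for inflammation will stop treatment with the study drug and will be promptly discontinued from the study". Section 6.2.3 likewise lists rescue among the mandatory reasons for discontinuation. The only later data are from an early termination visit, for which these subjects "should return within 7 days following the date that rescue medication begins". When that visit follows the start of rescue, LOCF does not use it.

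Section 8.1.2 defines the complete-resolution endpoints at each visit and also at the last visit on treatment. Change from baseline is defined only at each follow-up visit. Both the synopsis and 8.5.1.1 exempt it from the unadjusted visit-by-visit tests, and it is not in Table 3.

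**The concern.** A subject rescued at Visit 4 or Visit 5 has no observed grade at Visit 6, and LOCF fills the gap with the grade that made the eye eligible for rescue. At Visit 4 the previous visit is the baseline itself, so the carried change in the qualifying grade is zero or a worsening. An eye rescued at Visit 5 may carry some early improvement, but none since Visit 4.

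This amounts to assuming that such eyes would never have improved further. The plan does not assume that of vehicle eyes in general: every eye enters at Grade 2 or more, and 14.3% of vehicle eyes are expected to be cell-free at Day 8 (section 8.3.1). The scale is also coarse. Grade 2 covers 6 to 15 cells (Appendix B), so an unchanged grade can hide a falling count.

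If the arms differ in how many eyes are carried forward, the Day 15 difference in means partly reflects when subjects left rather than how inflamed the eyes would have been at that visit. The complete-resolution endpoints have a second method to set against LOCF; the mean scores have none. The general sentence offering two approaches does not supply one, because scoring a subject as a failure has no meaning for a mean change.

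**Working it through.** **1. The plan's own figures.** The plan states no figure for change from baseline, so the check starts with its power statement (section 8.3.1): 0.283 vs 0.143, 196 per group, two-sided 0.025.
- Pooled proportion: (0.283 + 0.143)/2 = 0.213.
- Null SE: √(2 × 0.213 × 0.787/196) = 0.0414.
- Alternative SE: √((0.283 × 0.717 + 0.143 × 0.857)/196) = 0.0407.
- z = (0.140 − 2.241 × 0.0414)/0.0407 ≈ 1.16, giving power of 87.7% (stated 87%).
- Simulating 250,000 trials with a shared vehicle group gives 95.9% for at least one difference (stated 95%) and 80.3% for both (stated 80%).

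The stated figures reproduce, and none of them depends on the LOCF rule.

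**2. Bias formula.** Let r be the share of an arm's eyes whose score is carried forward to Visit 6. Let g be the further mean fall in grade those eyes would have had by Visit 6 without rescue. Change is follow-up minus baseline, so a fall is negative. LOCF therefore raises an arm's mean change by r × g, and

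bias in (LE − vehicle) = r_LE × g_LE − r_V × g_V.

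A negative value overstates the benefit of LE.

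**3. Inputs.** The documents give no rescue or dropout rate by arm and no mean change. Every r and g below is an assumption.

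**4. More vehicle eyes carried forward, equal missed falls (grades).**

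| r_LE | r_V | g = 0.5 | g = 1.0 | g = 1.5 |
|---|---|---|---|---|
| 5% | 20% | -0.075 | -0.150 | -0.225 |
| 10% | 30% | -0.100 | -0.200 | -0.300 |
| 15% | 40% | -0.125 | -0.250 | -0.375 |

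Example: 0.05 × 0.5 − 0.20 × 0.5 = -0.075. Clearing from the minimum entry grade is a fall of 2 grades, so the range is about 4% (0.075/2) to 19% (0.375/2) of that.

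**5. Inputs that remove or reverse the bias.**
- Equal rates (20% and 20%) and equal falls: 0.
- 10% LE, 30% vehicle, falls 1.5 and 0.5: 0.15 − 0.15 = 0.
- 15% LE, 40% vehicle, falls 1.5 and 0.5: 0.225 − 0.20 = +0.025.
- 30% LE, 20% vehicle, equal falls of 0.5 to 1.5: +0.05 to +0.15.

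**6. What cancels it.** The bias is zero when g_LE/g_V = r_V/r_LE. At 10% and 30%, carried-forward LE eyes would have to miss three times the fall missed by vehicle eyes.

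**The case against.** The strongest objection is that the direction is not established. A reader might infer that LOCF must overstate LE. The documents do not support that: they give no rescue rates by arm, and step 5 shows bias of zero or of the opposite sign. Rescued eyes are also selected for not improving, so the average vehicle course need not apply to them, and 85.7% of vehicle eyes are not expected to be cell-free at Day 8. This stands, and it makes the conclusion conditional.

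A reader might also infer an inflated false-positive rate. The plan exempts this endpoint from visit-wise testing and names no test for it, so no planned decision is affected.

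It can be said that the pre-rescue grade is the right value if the target is the effect while on study drug. That is coherent, but the plan does not name this target. It provides a last-on-treatment value for the complete-resolution endpoints and not for change from baseline.

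There is partial mitigation. The resolution endpoints also use failure imputation, treatment failures at Visit 5 are an endpoint, rescue therapy has its own table (8.5.4), and discontinuation reasons are tabulated by group (8.5.5). A reader could therefore see unequal exit, but not its effect on the mean scores. The wording that further analyses may appear in the statistical analysis plan permits a second method without committing to one.

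Finally, a repeated-measures model is not guaranteed to be right. It assumes missing-at-random given recorded grades, whereas rescue is partly at the Investigator's discretion and withdrawal for adverse events is possible. That is a reason to show it beside LOCF rather than treat it as the truth.

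**Conclusion.** The concern holds in a conditional form. LOCF is the only stated rule for these mean scores, and it carries the pre-rescue grade of eyes chosen for lack of improvement to Day 15. Measured against the effect without rescue, the Visit 6 difference is likely to be overstated if rescue or discontinuation is more frequent on vehicle and the missed falls are similar. More rescue on vehicle is plausible because the plan assumes about twice the clearance on LE (0.283 vs 0.143), but it is not stated. The illustrative size is -0.075 to -0.375 grade, resting wholly on assumed rates and falls.

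The point concerns Visit 6. The synopsis places efficacy assessment at Visits 4 to 6, and Visit 7 is a post-treatment exam. The endpoint is secondary and outside the gatekeeping. The primary analysis uses failure imputation, so neither it nor the stated power is touched. Severity is low: a cheap improvement.

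**What to change.** In section 8.5.1.1 and the matching synopsis text:
- State the target for change from baseline: the LE-minus-vehicle difference at the visit, without rescue.
- Add a repeated-measures model for each score (cells, flare, composite) on all pre-rescue scores at Visits 4 to 6. Include treatment, visit, treatment by visit, Visit 3 score and Visit 3 score by visit, with unstructured covariance.
- Report LE-minus-vehicle differences with 95% intervals by visit, beside the LOCF table.
- Tabulate rescue by arm and visit.

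The cost is wording plus one standard model per score, with no new data, visits or subjects. The downsides are reliance on missing-at-random when rescue is partly discretionary, and a Day 15 difference that may be smaller than under LOCF.

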## 1.0 INTRODUCTION

Topical corticosteroids are useful in a variety of ophthalmic conditions and are generally indicated for treatment of steroid-responsive inflammatory conditions of the palpebral and bulbar conjunctiva, cornea, and anterior segment of the globe. Although corticosteroids are widely used as topical agents for ocular inflammation, most possess a risk profile that limits their general utility. A common risk associated with corticosteroid therapy is an elevation of intraocular pressure (IOP). Additionally, steroids may result in the development of cataracts or may increase susceptibility to bacterial and fungal infection.

Loteprednol etabonate (LE) is a corticosteroid that has been designed according to the 'retrometabolic design' concept. Such drugs are designed to provide maximal therapeutic effects with minimal side effects. This goal is achieved by synthesizing the drug from a known inactive metabolite of a known active drug. The inactive metabolite is then structurally modified to an active form that will undergo a predictable 1-step transformation back to the inactive metabolite *in vivo*. Loteprednol etabonate is the 17B-chloromethyl ester of  $\Delta^1$  - cortienic acid, an inactive metabolite of prednisolone.

Loteprednol etabonate exerts ocular anti-inflammatory effects when applied topically and undergoes a predictable metabolic deactivation process by enzymes that are found both in the eye and systemic circulation. This rapid metabolism reduces the propensity of LE to elevate IOP because the inactive metabolites of LE are unable to interact with the glucocorticoid receptor, through which corticosteroid effects on IOP are mediated.

Loteprednol etabonate has been approved by the United States (US) Food and Drug Administration (FDA) as well as other global health authorities both as a single agent drug and as a fixed combination suspension for several clinical indications (cf, Lotemax® [loteprednol etabonate ophthalmic suspension, 0.5%], Lotemax® [loteprednol etabonate ophthalmic gel, 0.5%]), Alrex® [loteprednol etabonate ophthalmic suspension, 0.2%], Zylet® [loteprednol etabonate 0.5% and tobramycin 0.3% ophthalmic suspension], and Lotemax® ointment [loteprednol etabonate ophthalmic ointment, 0.5%]). Clinical trial data have confirmed that the ophthalmic suspensions are well-tolerated by the eye and are efficacious in treating ocular inflammation. Loteprednol etabonate ophthalmic suspensions, in various concentrations, have been proven effective in several indications, including seasonal allergic conjunctivitis, giant papillary conjunctivitis, uveitis, and postoperative inflammation. Additionally, in clinical studies, LE ophthalmic suspension, 0.5% (Lotemax) has been shown to have a decreased incidence of significant IOP increase compared to prednisolone acetate. Thus, LE may offer a therapeutic advantage over conventional steroids by providing efficacy while reducing the risk for steroid-induced elevation of IOP.

Bausch + Lomb has formulated LE into a gel (loteprednol etabonate ophthalmic gel, 0.5% [Lotemax® gel, 0.5%]), a non-settling formulation which affords uniform distribution of the drug throughout the product. At room temperature and under low shear, the product behaves like a gel. The gel formulation converts to a fluid under the shear forces experienced upon squeezing through the tip of the dispenser bottle. Following dosing, the contents of the bottle immediately reestablish the gel structure while the electrolytes in the tear fluid inhibit reformation of the gel

structure on the surface of the eye. Lotemax® gel 0.5% therefore yields a consistent dose to the patient without the need to shake the bottle and is formulated to have a more neutral pH than Lotemax® suspension. Additionally, during the development of the Lotemax® gel 0.5% formulation, it was determined that the level of benzalkonium chloride (BAK) required to provide preservative effectiveness in this formulation (30 ppm) was well below that typically used in ophthalmic products, including Lotemax® suspension (100 ppm). This reduced level of BAK is expected to improve tolerability of the gel formulation. Lotemax® gel, 0.5% is approved for the treatment of post-operative inflammation and pain following ocular surgery. Clinical trial data have confirmed that this gel formulation is well-tolerated and efficacious in treating postoperative inflammation.

Bausch + Lomb has recently developed an improved ophthalmic formulation of LE, loteprednol etabonate ophthalmic gel, 0.38% (LE gel 0.38%) in which the particle size of the drug is smaller (in the submicron range). The smaller particle size in the gel formulation serves to increase ocular penetration and residence time in anterior segment tissues while retaining many of the advantages of the current LE gel, 0.5% formulation. An ocular PK study conducted in rabbits (Bausch + Lomb study BL13001) demonstrated that the new, lower concentration (0.38%) formulation provides similar or greater exposure to LE in anterior segment tissues compared to Lotemax® gel, 0.5%. In a separate study (Bausch + Lomb study 2013-GMP-042), systemic exposure to LE was evaluated in rabbits following ocular administration of LE gel, 0.38%. While the results of this investigation indicated that systemic exposure to LE was greater with the 0.38% LE gel formulation compared to Lotemax gel, 0.5%, overall, systemic exposure was very low. These PK results suggest that LE gel 0.38% is likely to be effective at treating ocular inflammation while providing a similar safety profile as Lotemax gel, 0.5%. The possible greater risks associated with higher anterior ocular tissue concentrations of loteprednol have been addressed by conduct of a 28-day GLP rabbit toxicology study with LE gel 0.38% that has shown negligible local or systemic toxicology findings compared to placebo. In addition, a human PK study is planned to asses the degree of systemic exposure to loteprednol from the newer LE gel 0.38% formulation.

Additionally, in the interest of potentially improving patient dosing compliance, dosing frequency is addressed in the present clinical study. Loteprednol etabonate gel, 0.5% is indicated for QID dosing and the rabbit PK results with LE gel 0.38% have suggested less frequent dosing (eg, BID or TID) may be adequate to confer clinical efficacy. The present clinical study consequently is designed to examine whether this supposition is true; ie, whether BID dosing and/or TID dosing of LE gel 0.38% may be effective in reducing post-cataract surgery inflammation and pain.

